The outcome measures will be surgeon-specific and patient-specific. These outcome measures for the 'Trainee' group will commence following completion of the simulation training (if applicable), whereas they can commence immediately following study approval for the 'Expert' group. The surgeon-specific outcome measures will be the objective motion-analysis metrics generated by validated and extensively used wireless sensors placed on the elbows of surgeons under their sterile gowns during the operation; and subjective assessments of surgical trainee performance using validated and reliable forms of structured human grading. Patient-specific outcome measures will be collected for a pre-determined number of patients who have undergone a primary elective THR by any of the surgeon participants in this study. All patient-specific outcome measures (with the exception of a post-operative questionnaire) are routinely collected as part of the patients NHS clinical care, and no other additional investigations are required for conducting this research. All patients will be asked to provide their written informed consent for the use of their data in this study. The patient-specific outcome measures include: pre- and post-operative blood tests and radiograph (X-ray) analysis; the incidence of blood transfusions and any other peri-operative complications; the in-patient length of stay; and two patient-reported outcome measure (PROMs) questionnaires.

Statistical analysis will then be performed on the data collected, specifically aiming to identify any significant differences in either surgeon performance metrics, or patient outcome measures between:

- 1) The StR's who have undertaken additional simulation training versus those who have routine Deanery training.
- 2) The 'Trainee' group and the 'Expert' group. A sub-group analysis may be performed within the 'Expert' group also to determine any differences between the Consultants and Fellows.

In summary, this novel research will use validated methodology and routinely collected patient outcome measures in order to determine the impact of simulation training on surgical trainee performance and patient outcomes following a primary elective THR, and also help to benchmark an expert level of performance in this commonly performed and highly effective operation. The results of this study will hopefully help in shaping the future of orthopaedic surgical training and assessment within the United Kingdom.

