9.4 Randomisation

Randomisation will be performed via a blinded sealed envelope containing information regarding which arm of the study they will participate in. As we only anticipate recruiting 2 StR's from each recruitment centre every 6 months, a more complex allocation/randomisation procedure will not be required. Over the 18 to 24-month study period we aim to recruit and randomise 6-8 StR's to the 'intervention' group, and randomise 6-8 StR's to the 'control' (routine training) group, with an even distribution of these StR's in both groups across the two recruiting hospital sites.

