9.5 Blinding and code-breaking

Standard surgical practise will be followed. Patients are not formally blinded to which Surgeon (Consultant, Fellow, or StR) performs their operation, and are informed if requested. In line with standard surgical practise and training within the NHS, patients will provide informed consent that they understand no guarantees can be given that a particular person will perform the procedure. The person will, however, have appropriate experience.

Due to the nature of this study the StR's cannot be blinded to their allocations into either the 'control' or 'intervention' groups, however the assessment methods and any assessors will be blinded.

9.6 Description of study intervention(s),

The intervention to be tested is the simulation-based and cognitive learning package, which will be delivered to a randomised sub-group of 50% of the StR's recruited into this study. This will be delivered in a supervised setting within the OOSEC over a 4-week period for between 1 to 2 hours per week, over 3 to 4 consecutive but separate six-month placements (please see Appendix A for Study Flow Diagram). This will take place on a Wednesday afternoon, which is when all the Regional StR's are due to attend teaching in Oxford at the NOC.

The OOSEC is a secure enclosed laboratory space within the NOC, which contains all the necessary equipment required to run the simulation-based and cognitive learning training. The simulation training in general may include:

- 1) Focussed workshops on saw-bone models (simulated bones)
- 2) Digital and computer-based cognitive learning packages
- 3) Virtual reality platforms.

All participants within group 1 (StR's) will be asked to attend and complete baseline and final assessments within the OOSEC, which will consist of a multiple-choice questionnaire (MCQ) and a simulated procedure. Participants within group 2 (Consultants and Fellows) will only be required to complete a baseline simulated procedure.

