11 STATISTICS AND ANALYSIS

Analysis of motion data.

Motion data from the wireless sensors produces performance surrogate markers such as: the number of movements (major & minor); total path length; and smoothness/economy of movement. Data distributions will be assessed for normality using the Shapiro-Wilk test. Previous studies show such data are not normally distributed, and we would expect to use non-parametric tests, such as the Mann-Whitney U test to compare the performance metrics between the 2 groups of participants (StR's against Experts & Fellows). The Mann-Whitney U test will also be used to compare performance metrics between the two sub-groups of StR's (control and intervention), and also within the intervention sub-group in order to compare performance before and after training.

Performance metrics within all groups of participants will be reported using descriptive statistics to outline the central tendency (mean, median, and mode) and variation (range, variance, and standard deviation) in readings obtained. The Kruskal-Wallis one-way analysis of variance (ANOVA) test will be used to test for differences in the mean values obtained for all performance metrics between the two groups of participants. The Wilcoxon signed-rank test will be used to determine any differences in performance metric between the two groups.

Analysis of other routinely obtained data

X-ray (radiograph) analysis:

X-rays will be reviewed by two independent Consultant Orthopaedic Surgeons who will be blinded to the patient and lead surgeon's identity in order to reduce bias. There are several important parameters to be evaluated when reviewing a pelvic x-ray, therefore we will ask each reviewer to allocate a categorical global rating (see below) for both the pre- and post-operative x-rays. [5] The Chi-squared test will be used

to determine if there are any significant differences between each group, and also intra-group differences (for example StR's before and after additional training).

Pre-operative x-ray

- 1: Hip osteoarthritis without significant bone loss.
- 2a: Hip osteoarthritis with significant bone loss on acetabular side.
- 2b: Hip osteoarthritis with significant bone loss on femoral side.
- 3: Hip osteoarthritis with significant bone loss on both acetabular and femoral sides.

Post-operative x-ray

- 1: Excellent implant position and restoration of hip anatomy.
- 2a): Good overall with minor imperfections on acetabular side.

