- 2b): Good overall with minor imperfections on femoral side.
- 3: Moderate concerns but does not require revision surgery.
- 4: Significant concerns requiring revision surgery.

Every patients post-operative x-ray will also be reviewed by the PI ([name]) for acetabular component positioning (inclination and version) using the methodology described by Bachhal [4]. This continuous data will be assessed for normality of distribution, and analysed using similar methodology as described above for the motion data. We will be looking for any statistically significant differences between the 2 groups of participants, within the two sub-groups of StR's (control and intervention), and also within the intervention sub-group in order to compare performance before and after additional training.

Other outcomes data:

Following collection of the outcome measures listed below, the normality of the data distribution will be checked with the Shapiro-Wilk test. Descriptive statistics will be used to outline the central tendency and variation of these data sets. Statistical analyses between each group of participants will be performed using either the parametric unpaired t-test or a non-parametric Mann-Whitney U test depending on the distribution of the data. Subsequent analysis of the outcomes data using a paired t-test, or Mann-Whitney U test will also be performed within the two sub-groups of the StR's (control and intervention), and also within the intervention sub-group in order to compare outcomes before and after additional training.

- Theatre time usage.
- Blood loss (pre-/post-op haemoglobin levels)
- In-patient length of stay.
- PROMs: EQ-5D and OHS.

The Chi-squared test (or Fishers exact test if the sample is <5) will be used to determine any significant differences between the groups regarding the incidence of blood transfusions or peri-operative morbidity.

All of these tests will be performed using the SPSS statistical package, which is available for any registered student on the University of Oxford current Licencing agreement.

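### Section 11 gives the unpaired Mann-Whitney test to the before/after comparison within the trained registrars and the paired signed-rank test to different surgeons; the two look interchanged

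*Combined protocol and SAP*

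**What the plan says.** Three statements in section 11 matter.

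- **Motion data, first paragraph.** "The Mann-Whitney U test will also be used to compare performance metrics between the two sub-groups of StR's (control and intervention"), and the sentence goes on to apply the same test "also within the intervention sub-group in order to compare performance before and after training".
- **Motion data, second paragraph.** "The Wilcoxon signed-rank test will be used to determine any differences in performance metric between the two groups". The groups just named there are groups of participants, so they contain different surgeons.
- **Other outcomes data.** "Subsequent analysis of the outcomes data using a paired t-test, or Mann-Whitney U test will also be performed" within the two StR sub-groups, and within the intervention sub-group before and after training. The outcomes listed are theatre time, blood loss, length of stay and PROMs.

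On numbers, section 9.4 says "we aim to recruit and randomise 6-8 StR's to the 'intervention' group"; the synopsis has 8.

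On what is measured twice, section 9.6 says "All participants within group 1 (StR's) will be asked to attend and complete baseline and final assessments within the OOSEC", made up of a multiple-choice paper and a simulated procedure. Section 9.2 places the baseline assessment after randomisation, and section 9.3 places the final one at 3 months into the placement. The lay summary says of the surgeon and patient outcome measures: "These outcome measures for the 'Trainee' group will commence following completion of the simulation training (if applicable"). Section 9.3 likewise puts the intervention group's intra-operative assessments after training.

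**The concern.** A before value and an after value from one registrar are not independent. Mann-Whitney ignores the link and leaves stable skill differences between registrars in the noise. Signed-rank works on each registrar's own change and removes them. With 6 to 8 registrars this can decide whether a real improvement is detected.

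The reverse error sits in the next paragraph. Signed-rank cannot sensibly be run between different surgeons, because no rule links a surgeon in one group to a surgeon in the other. An analyst who follows the text literally would apply the wrong test in both places.

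The other-outcomes sentence has a related fault. It sets Mann-Whitney beside the paired t-test, although the rank counterpart of the paired t-test is signed-rank.

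**Working it through.** **Inputs from the plan.** Pairs: 6-8 (section 9.4). Tests: as set out above. The plan states no alpha, power, effect size or before/after correlation for this comparison, so there is no planned figure to reproduce.

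**Assumptions.** Two-sided 5% with exact critical values; change d from 0.5 to 1.5 SD of a single score; correlation ρ from 0 to 0.9; bivariate normal scores. A lognormal version gave power within about 0.04.

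**Why pairing matters.** For n registrars and single-score SD σ, the variance of the mean change is 2σ²(1−ρ)/n. An independent-samples test behaves as if it were 2σ²/n. With n = 8 and σ = 1:

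- treated as independent: 2/8 = 0.25, SE 0.50
- ρ = 0.5: 2(0.5)/8 = 0.125, SE 0.354
- ρ = 0.7: 2(0.3)/8 = 0.075, SE 0.274

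The unpaired test therefore uses too large a standard error whenever ρ > 0, which makes it conservative.

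**Exact critical values.**

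- n = 8: Mann-Whitney rejects at U ≤ 13 (size 0.0499). Signed-rank rejects at W ≤ 3; five rank subsets have a sum of at most 3, so its size is 2 × 5/2⁸ = 0.0391.
- n = 6: signed-rank rejects only if all six changes have the same sign, p = 2/2⁶ = 0.031.

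**Simulated power, n = 8, d = 1** (40,000 data sets per cell, Monte Carlo SE at most 0.0025). Relative loss = 1 − (Mann-Whitney power / signed-rank power).

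| ρ | Mann-Whitney | Signed-rank | Relative loss | Mann-Whitney rejection under no change |
|---|---|---|---|---|
| 0 | 0.439 | 0.347 | none (Mann-Whitney ahead) | 0.051 |
| 0.3 | 0.437 | 0.466 | 6% | 0.024 |
| 0.5 | 0.437 | 0.610 | 28% | 0.012 |
| 0.7 | 0.441 | 0.824 | 46% | 0.004 |
| 0.8 | 0.454 | 0.942 | 52% | 0.001 |

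**Other effect sizes, n = 8.**

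- d = 0.5, ρ = 0.9: 0.043 against 0.709, loss 94%
- d = 0.8, ρ = 0.9: 0.245 against 0.980, loss 75%
- d = 1.5, ρ = 0.7: 0.867 against 0.990, loss 12%

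**n = 6, d = 1.** At ρ = 0.7 power is about 0.27 against 0.54. At ρ = 0.3 Mann-Whitney is slightly ahead, 0.28 against 0.26.

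**Which measures have a before value.**

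| Measure | Before training | After training |
|---|---|---|
| OOSEC multiple-choice paper and simulated procedure | yes (9.2, 9.6) | yes (9.3, 9.6) |
| Intra-operative motion metrics and ratings | none planned (lay summary, 9.3) | yes |
| Patient outcomes, including x-rays | none planned (lay summary, 9.3) | yes |

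Only the first row can supply one before and one after value per registrar.

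**The case against.** The strongest reply is that the pairs are not fully documented. Section 11 is writing about motion metrics, while sections 9.7 and 12 place the sensors in theatre. Section 9.6 does not say that they are worn for the simulated procedure. This stands. A reader might infer that the OOSEC procedure supplies paired motion data, but the documents do not say so. It limits where the comparison can be made; it does not make Mann-Whitney suitable for repeated scores on the same people.

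A second reply concerns the other-outcomes sentence. A reader might infer that a normality check decides whether pairing is used. The text does not establish that: the rule about distribution belongs to the preceding sentence, and the sentence at issue covers two comparisons, so its two tests may belong to different ones. The outcomes listed also come from patients. Any before and after patients would be different people, several per registrar, with no natural one-to-one match. Deleting Mann-Whitney there and leaving a paired t-test would not help.

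Third, the signed-rank sentence shows that the authors had the paired rank test in mind, so this may be a slip of drafting. That is plausible and makes the repair easy. Even so, the text as it stands directs the analyst to the wrong test.

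**Conclusion.** Wrong as written, and correctable. The misassignment can be read directly from section 11 and needs no simulation. Its cost depends on two quantities that the plan does not give. For 8 pairs and a 1-SD change, power is about 0.44 instead of 0.61 at correlation 0.5, or 0.82 at correlation 0.7. At correlation 0.3 or below there is little or no gain from pairing.

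Three stronger readings are not supported:

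- **That the loss is capped at about half.** There is no such bound. Across the assumed ranges it runs from none to 94%.
- **That false positives are inflated.** With positive correlation the error is in the conservative direction; the risk is a missed change.
- **That the trial's main comparison is compromised.** The before/after test is a within-arm comparison. For control against intervention, section 11 names Mann-Whitney for the motion metrics, which is a test for different surgeons, so this point leaves the randomised contrast untouched.

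**What to change.** **Section 11, motion data.** Test the within-StR change, using one before and one after value per registrar, with the exact Wilcoxon signed-rank test. Keep Mann-Whitney for comparisons between different surgeons. Remove signed-rank from the sentence on differences between the two groups.

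**Section 11, other outcomes data.** Name signed-rank as the non-parametric counterpart of the paired t-test, and allow either paired test only where one before and one after value per StR exists.

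**Scope of the before/after comparison.** Limit it to measures taken at both the baseline and final OOSEC assessments, and list those measures, stating whether motion metrics are among them. Drop it for intra-operative metrics and for patient outcomes, including the x-ray comparisons, because no before value is planned for these.

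**Cost.** Wording changes in section 11 only, with no new data. If 6 registrars are trained, the text should note that signed-rank reaches two-sided 5% only when all six change in the same direction.

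### Section 11 applies a paired test to independent groups of surgeons, and plans before/after-training analyses of operative and patient outcomes for which the visible text describes no pre-training operations

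*Combined protocol and SAP*

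**What the plan says.** Under the motion-data heading, Section 11 assigns the Mann-Whitney U test "to compare the performance metrics between the 2 groups of participants (StR's against Experts & Fellows"). It assigns the same test to control against intervention registrars, "and also within the intervention sub-group in order to compare performance before and after training". The next paragraph adds: "The Wilcoxon signed-rank test will be used to determine any differences in performance metric between the two groups".

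Before/after-training comparisons then recur for three further sets of outcomes:

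- **X-ray grade:** a chi-squared test is to cover "intra-group differences (for example StR's before and after additional training").
- **Cup inclination and version:** these are to be "analysed using similar methodology as described above for the motion data", "also within the intervention sub-group in order to compare performance before and after additional training".
- **Theatre time, haemoglobin, length of stay, EQ-5D and OHS:** "Subsequent analysis of the outcomes data using a paired t-test, or Mann-Whitney U test will also be performed within the two sub-groups" of registrars, "also within the intervention sub-group in order to compare outcomes before and after additional training".

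On timing, Section 2 (Lay Summary) has trainee outcome measures, both surgeon-specific and patient-specific, begin once any simulation training is finished. Section 9.3 places the intervention arm's eight theatre assessments after that training. Sections 9.2 and 9.6 describe a baseline assessment in the simulation centre (OOSEC), made up of a multiple-choice paper and a simulated procedure.

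**The concern.** There are three linked problems.

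(a) A paired test is prescribed for groups made up of different people.

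(b) Eight outcomes that arise only from operations on patients are to be compared before and after training, yet the schedule as written supplies operations only after it.

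(c) Tests and data layouts do not line up. The one motion comparison made within the same trainees is given an unpaired test. For the other outcomes, a paired and an unpaired test are offered side by side without saying which serves which comparison.

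The effect of training is the primary objective. If the text stands, an analyst must either ignore parts of Section 11 or supply a pairing or a before period that the protocol does not define.

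**Working it through.** **Group sizes.** Section 3 gives 16 registrars (8 + 8), 8 Fellows and 5 Consultants. The plan's patient total confirms these counts: 16 × 8 + 8 × 5 + 5 × 5 = 128 + 40 + 25 = 193, as stated. Experts and Fellows together number 8 + 5 = 13.

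**(a) Can a signed-rank test be formed?** It ranks the differences dᵢ = xᵢ − yᵢ, so each xᵢ must have its own yᵢ.

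| Reading of the two groups | Sizes | Pairing described | Result |
|---|---|---|---|
| Registrars v Experts and Fellows | 16 v 13 | none | cannot be formed; software rejects the unequal lengths |
| Control v intervention registrars | 8 v 8 | none (parallel 1:1 randomisation) | runs only after an arbitrary pairing |

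Eight surgeons can be paired with eight others in 8! = 40,320 ways. As an illustration, one 8 v 8 dataset was simulated from assumed lognormal distributions and re-paired at random 5,000 times. The signed-rank p-value ran from 0.008 to 0.31 on the same data, whereas Mann-Whitney U gave a single value, 0.050.

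**(b) Is there a before period?** The outcomes with a planned before/after-training comparison, outside motion, are X-ray grade (1), cup inclination and version (2), and theatre time, haemoglobin, length of stay, EQ-5D and OHS (5): 1 + 2 + 5 = 8.

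| Place | What it says on timing |
|---|---|
| Section 2 | trainee outcomes, surgeon and patient, start after training |
| Section 9.3 | intervention-arm theatre assessments (8 in total) follow training |
| Sections 9.2, 9.6 | baseline is a written paper and a simulated procedure in the laboratory |
| Sections 3, 6 | outcomes collected for all patients of a participating lead surgeon; no start date |
| Appendix A | flow chart not shown in the text available |

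A laboratory paper and a simulated procedure yield none of the eight outcomes. Pre-operative X-rays, haemoglobin and questionnaires precede a patient's surgery, not the surgeon's training, so they do not fill the gap. The visible text therefore describes a pre-training source for 0 of the 8. For motion data, the simulated procedure might provide a before value, but nothing says that the sensors are worn for it.

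**(c) Does the mismatch matter where real pairs exist?** Take 8 surgeons measured before and after, with assumed normal data, a two-sided 5% level and an assumed within-surgeon correlation (4,000 simulations each):

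| Correlation | Type I error, Mann-Whitney | Type I error, signed-rank | Power at 1-SD shift, Mann-Whitney | Power at 1-SD shift, signed-rank |
|---|---|---|---|---|
| 0 | 0.050 | 0.044 | 0.44 | 0.34 |
| 0.5 | 0.013 | 0.037 | 0.44 | 0.61 |
| 0.8 | 0.002 | 0.050 | 0.45 | 0.94 |

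With correlated per-surgeon values, the unpaired test is conservative and loses power. The correlations and the shift are assumptions, and the table applies only if the unit is the surgeon.

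**The case against.** The strongest reply is that the signed-rank sentence is surplus. Section 11 already gives both motion contrasts to Mann-Whitney U, and gives group comparisons of the other outcomes to an unpaired t-test or Mann-Whitney. That stands: ignoring the sentence costs the randomised comparison nothing. Its spread to cup position is also only possible, since the text there refers loosely to similar methods.

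A second reply is that the objectives tables in Sections 3 and 6 cover all patients with no start date, that Section 2 is only a lay summary, and that the flow chart cannot be seen. This stands in part. No order of precedence is stated, so the passages need reconciling. But a missing start date does not describe a pre-training period, and Section 9.3 agrees with Section 2.

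A reader might be tempted to go further in four ways that the documents do not support:

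- **That the patient numbers prove no pre-training cases exist,** because eight patients per registrar equal eight post-training assessments. Eight operations is a minimum and 193 is an estimate, so subtracting one from the other proves nothing.
- **That the week-6 start in Section 7 shows every assessment follows training.** Section 7 never says when in the placement training begins.
- **That the paired t-test or Mann-Whitney sentence must name a wrong test.** It covers two comparisons and could intend one test for each. The fair charge is that it is unclear.
- **That Kruskal-Wallis on two groups is a further error.** It is redundant with Mann-Whitney, not harmful.

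**Conclusion.** Section 11 is wrong as written on two counts and unclear on a third.

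- **Signed-rank test:** it does not fit either between-group contrast. There are no described pairs at 16 v 13 or at 8 v 8.
- **Before/after-training analyses:** for all eight operative and patient outcomes they conflict with Sections 2 and 9.3, and the visible text describes no pre-training operation.
- **Test assignment:** the same-trainee motion comparison is given an unpaired test, and the sentence on other outcomes does not say which test serves which comparison.

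A reader might infer that the main contrasts cannot be analysed. They can, because a suitable unpaired test is already named for each. The point deserves correction before analysis but does not threaten the randomised comparison.

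The conclusion on before/after data rests on the visible text and assumes that Appendix A describes no pre-training operations. The conclusion on the signed-rank test needs no assumption beyond the absence of any stated matching.

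**What to change.** 1. Delete the signed-rank test from every between-group contrast, say explicitly that it does not extend to cup position, and keep the unpaired test already named.
2. Delete the before/after-training analyses of X-ray grade, cup position, theatre time, haemoglobin, length of stay, EQ-5D and OHS, and rely on the randomised between-arm comparison. If they are to stay, the protocol must identify an actual source of pre-training operations and be reconciled with Sections 2, 3, 6 and 9.3 and Appendix A.
3. Limit before/after-training analysis to the OOSEC baseline and final assessments, with a paired test on one value per surgeon. If motion metrics are to be included, Section 9.6 should say that sensors are worn there.
4. For the other outcomes, state one test per comparison: unpaired between arms, paired only where real pairs exist, such as a patient's own pre- and post-operative values.

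The cost is a rewording of Section 11, plus a sentence in Section 9.6 if motion is kept in the laboratory comparison. No new patients or data are needed. The downside is that before/after claims on operative and patient outcomes are lost. Keeping them would mean describing, and perhaps adding, pre-training data collection.

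### The Chi-squared test on the X-ray rating ignores the order of the grades and the grouping of hips by registrar; an ordinal comparison that allows for registrar is a cheap improvement

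*Combined protocol and SAP*

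**What the plan says.** Section 11 (X-ray analysis) has two independent consultant surgeons, blinded to patient and lead surgeon, give each film a "categorical global rating (see below) for both the pre- and post-operative x-rays". For differences between groups, and within groups, "The Chi-squared test will be used"; no other test is named for this rating.

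The post-operative scale has five labels:
- best grade: "1: Excellent implant position and restoration of hip anatomy"
- grade 2a, which gives the same verdict as 2b but for the acetabulum
- the femoral counterpart: "2b): Good overall with minor imperfections on femoral side"
- grade 3, for films that raise moderate worry without a need to revise
- worst grade: "4: Significant concerns requiring revision surgery"

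The same section names the Mann-Whitney test for several other outcomes. It does not say how the two readers' grades are combined, and it does not mention that several patients share a surgeon. Sections 3 and 6 list X-ray analysis among the measures under the primary objective.

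**The concern.** The labels form a scale of quality. Grades 2a and 2b share the same verdict and differ only in the side of the imperfection, so they are one level split in two. That leaves four ordered levels. Pearson's Chi-squared gives the same p-value however the labels are shuffled. On five categories and two arms it spends (5 − 1) × (2 − 1) = 4 degrees of freedom on any kind of difference, whereas the trial asks whether training makes results better.

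The test also counts each hip as a separate unit, although registrars, not patients, are randomised. If registrars differ in skill, the hips of one registrar resemble each other and the nominal 5% no longer holds.

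At stake are power for a shift along the scale, the error rate of the randomised comparison, and whether the report carries an estimate that a reader can interpret.

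**Working it through.** **Inputs from the documents.** Section 3: 8 patients per registrar. Sections 3 and 7: 8 registrars per arm, randomised 1:1. Section 8.1: possibly only 12 to 16 registrars in all.

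**The plan's own figure.** 16 × 8 + 8 × 5 + 5 × 5 = 128 + 40 + 25 = 193, as stated. It is a head count. No power, effect size, alpha or expected grade distribution is given for this or any other outcome, so there is no stated power to reproduce.

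**Hips per arm.** 8 × 8 = 64 with 16 registrars; 6 × 8 = 48 with 12.

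**Assumptions.** Two-sided 5%; a proportional-odds shift; six control distributions over 1/2a/2b/3/4, with grade 1 at 20 to 70% and grade 4 at 1 to 5%.

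**Step 1: independent hips.** Simulated power of Chi-squared on five categories against a tie-corrected Mann-Whitney test with 2a and 2b tied, 64 v 64, control grades 50/20/15/12/3%:

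| Odds ratio | Chi-squared | Rank test |
|---|---|---|
| 2 | 29% | 50% |
| 2.5 | 49% | 72% |
| 3 | 65% | 86% |

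Over all six distributions the shortfall is 16 to 25 points at odds ratios 2 to 3, and 6 to 25 points over 1.5 to 4. At 48 v 48 it is 15 to 25 and 7 to 26 points. Merging 2a and 2b but keeping Chi-squared recovers only about 4 to 7 points at odds ratios 2 to 3, so most of the loss comes from ignoring order.

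**Step 2: hips grouped by registrar.** The documents give no intraclass correlation (ICC); 0.05 to 0.10 is assumed. The variance inflation for a mean of 8 hips is 1 + (8 − 1) × ICC, which is 1.35 at 0.05 and 1.70 at 0.10. Simulated rejection under no effect:

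| Method | Rejects under no effect |
|---|---|
| Chi-squared on hips | about 5 to 9% |
| Rank test on hips | 8 to 13% |
| Registrar mean grade, 8 v 8 | 4 to 6% |

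**Step 3: power of a method that respects registrars.** Registrar mean grade (t-test, 8 v 8) against Chi-squared, control grades 30/20/20/25/5%:
- No clustering: a gain of 8 to 14 points at odds ratios 2 to 3.
- ICC 0.05: 38% v 37% at odds ratio 2, 58% v 54% at 2.5, 73% v 71% at 3.
- ICC 0.10: 29% v 35% at odds ratio 2.

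With clustering, the Chi-squared figures are nominal, because its error rate is above 5%. The proportional-odds model with a registrar random effect was not simulated.

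**Step 4: an effect on one side only.** From control grades 50/20/15/12/3%, moving 15 points from 2a to 1 gives Chi-squared 55% and the rank test 28%. Moving 15 points from 2a to 2b gives 68% and 4.5%.

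**The case against.** The plan calls the rating categorical and splits the middle grade by side. A sponsor could say that this is deliberate, since training might change cup placement and not stem placement. That stands in part: Step 4 shows that Chi-squared can win when one side alone changes. But a swap from 2a to 2b is not an improvement in quality, and the side can still be tabulated.

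Four stronger readings are tempting, and the documents do not support them.
- **That the plan loses about 20 points of power, which the fix would recover.** No document figure supports one number. The 16 to 25 points belong to a rank test on independent hips, which is the method with the worst error rate once hips are grouped.
- **That sparse cells make the test invalid.** Grade 4 at an assumed 5% gives 64 × 0.05 = 3.2 hips per arm, and at least one expected count falls below 5 in 80 to 100% of simulated tables. Yet without clustering Chi-squared rejects only about 4 to 5% under no effect. The Fisher fallback in section 11 covers only transfusion and morbidity, but that does no measurable harm here.
- **That a significant result would have no direction.** Only the p-value lacks it; the grade percentages by arm would show it.
- **That this is the trial's only blinded rating.** Section 9.5 says that assessors will be blinded in general.

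The rating is also one of several unpowered measures under the primary objective, which limits the weight of the point.

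**Conclusion.** The point holds as a cheap improvement to section 11. The planned test ignores an order that is plain in the grade labels, from "1: Excellent implant position and restoration of hip anatomy" to "4: Significant concerns requiring revision surgery", and takes no account of the registrar, who is the randomised unit.

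If hips were independent and training shifted grades by a common odds ratio of 2 to 3, the cost of ignoring order would be about 16 to 25 points of power against a rank test. With a registrar ICC of 0.05 to 0.10, a method that respects registrars has power similar to or lower than the nominal power of Chi-squared. What it gains is an error rate near 5% and an estimate with a direction. All of these sizes rest on assumed grade distributions, effects, alpha and ICC. The two defects themselves rest on the text alone.

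**What to change.** In section 11, for the randomised comparison of registrars:
1. Tie 2a and 2b as one level of the post-operative grade.
2. Compare arms by the registrar's mean post-operative grade, or by a proportional-odds model with a registrar random effect and the pre-operative grade as a covariate. Name one of them in advance. With only 8 registrars per arm (perhaps 6), the registrar mean is the simpler choice, and its error rate was checked above.
3. Report the mean difference or the odds ratio with its confidence interval.
4. State how the two readers are used: for example, average their grades in the registrar mean, or include reader as a term in the model. No consensus reading is then needed.
5. Tabulate 2a and 2b separately by arm.

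The cost is a few sentences, with no new films, readings or patients. The downside is that the side of the imperfection leaves the test. If training changes one side only, merging can have less power than Chi-squared: 28% v 55% for a rank test on merged grades under the assumed shift from 2a to 1.
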